#### 14.13 Study summary report

After the end of the study, the investigator and the Fosun should objectively summarize the study results, statistically analyze the study data using appropriate statistical methods, make an objective evaluation of the drug safety based on the results, and prepare a written summary report of this clinical study after review and approval by the sponsor and Fosun.

# 14.14 Information disclosure and data publishing policy

The investigator should keep the information and data related to this study confidential and do not cite or publish relevant study results or data without the sponsor and Fosun's consent.

The sponsor and Fosun have the right to publish information or data related to this study, or report it to the regulatory authority. If the sponsor and Fosun need to display the name of the investigator in the publication or advertising content, it should obtain the investigator's consent.

# Appendix A WHO and CDC Website

- World Map indicating Areas with Risk of COVID-19: https://www.who.int/emergencies/diseases/novel-coronavirus-2019
- COVID-19 Map of China: http://2019ncov.chinacdc.cn/2019-nCoV/

# Appendix B NMPA Guidance for Adverse Events Grading Scale for Preventive Vaccine Clinical Trials in China

# Appendix B Table 1 Grading scale for vaccination site (local) adverse events

Symptoms/signs	Grade 1	Grade 2	Grade 3	Grade 4			
Pain and tendern	Pain and tenderness (optional; use tenderness for subjects who cannot express pain autonomously)						
Pain	Pain Do not affect or slightly affect physical activity		Affect daily life	Loss of basic self-care ability, or hospitalization			
Tenderness	Resist or flinch after touching	Cry after touching, but can be soothed	Cry continuously, unable to be soothed	Need emergency treatment or hospitalization			
Induration*, swelling**#	2.5 ~ <5 cm in diameter or 6.25 ~ <25 cm² in area and do not affect or slightly affect daily life	$5 \sim <10$ cm in diameter or $25 \sim$ $<100$ cm  in area or affect daily life	≥10 cm in diameter or ≥100 cm² in area or ulceration or secondary infection or phlebitis or sterile abscess or wound drainage or seriously affect daily life	Abscess, exfoliative dermatitis, dermal or deep tissue necrosis			
Rash*, blush ** #	2.5 ~ <5 cm in diameter or 6.25 ~ <25 cm² in area and do not affect or slightly affect daily life	$5 \sim <10$ cm in diameter or $25 \sim <100$ cm  in area or affect daily life	≥10 cm in diameter or ≥100 cm² in area or ulceration or secondary infection or phlebitis or sterile abscess or wound drainage or seriously affect daily life	Abscess, exfoliative dermatitis, dermal or deep tissue necrosis			
Others							
Pruritus	Pruritus at the vaccination site, resolved by itself or within 48 hours after treatment	Pruritus at the vaccination site, not resolved within 48 hours after treatment	Affect daily life	NA			

Symptoms/signs	Grade 1	Grade 2	Grade 3	Grade 4
Cellulitis	NA	Need for treatment other than injection (e.g. oral antibacterial, antifungal, antiviral drugs)	Need for intravenous therapy (e.g. intravenous antibacterial, antifungal, antiviral drugs)	Sepsis, or tissue necrosis, etc.

Note: \* In addition to directly measuring the diameter for graded evaluation, the progression changes of the measurement results should also be recorded.

#The evaluation and grading of induration and swelling, rash, and blush should be based on the functional level and actual measurement results, and select a higher grading index.

Appendix B. Table 2 Grading scale for vital signs

Signs	Grade 1	Grade 2	Grade 3	Grade 4
Fever* [Axillary temperature (°C)]	37.3~<38.0	38.0~<38.5	38.5~<39.5	≥39.5 for more than 3 days
ECG PR interval extension or atrioventricular block	PR interval 0.21 ~ <0.25 seconds	PR interval ≥0.25 seconds or second- degree atrioventricular block type I	Second-degree atrioventricular block type II or ventricular interval ≥ 3 seconds	Complete atrioventricular block
Signs	Grade 1	Grade 2	Grade 3	Grade 4
Heart rate				
Tachycardia (beats/minute)	101~115	116~130	>130	Arrhythmia requiring emergency treatment or hospitalization
Bradycardia (beats/minute)	50~54	45~49	<45	Arrhythmia requiring emergency treatment or hospitalization
Blood pressure				
Hypertension (mmHg)	Systolic blood pressure: 140 ~ <160 or diastolic blood pressure: 90 ~ <100	Systolic blood pressure: ≥160 ~<180 or diastolic blood pressure: ≥100 ~<110	Systolic blood pressure: ≥180 or diastolic blood pressure: ≥110	Occurrence of previously undiagnosed life-threatening complications (eg malignant hypertension) or hospitalization
Hypotension (systolic blood pressure) (mmHg)	85~<89	80~<85	<80	Shock or hospitalization
Respirator rate (times/minute)	17~20	21~25	>25	Intubation required

\*\* The maximum measured diameter or area should be used.

Note: \* Axillary temperature is usually adopted in China, and it can be converted into oral temperature and anal temperature if necessary. Generally, oral temperature = axillary temperature + 0.2 °C;

Anal temperature = axillary temperature +  $(0.3 \sim 0.5^{\circ}\text{C})$ . When persistent high fever occurs, the cause of high fever should be identified as soon as possible.

Appendix B. Table 3 Grading scale for non-vaccination site (systemic) reactions

Organ system symptoms/signs	Grade 1 Grade 2		Grade 3	Grade 4		
Gastrointestinal system						
Diarrhea	Mild or transient, 3 to 4 times/day, abnormal fecal appearance, or mild diarrhea lasting less than 1 week	Moderate or persistent, 5-7 times/day, abnormal fecal appearance, or diarrhea> 1 week	>7 times/day, abnormal fecal appearance, or hemorrhagic diarrhea, orthostatic hypotension, electrolyte imbalance, needing intravenous infusion> 2L	Hypotension shock, needing hospitalization		
Constipation*	Stool softener and diet adjustment needed	Laxative medications needed	Stubborn constipation requiring manual defaecation or enema	Toxic megacolon or intestinal obstruction		
Dysphagia	Mild discomfort when swallowing	Restricted diet	Diet and conversation are very limited; cannot eat solid food	Cannot eat liquid food; intravenous nutrition needed		
Anorexia	Loss of appetite, food intake not reduced	Loss of appetite, reduced food intake, but no significant weight loss	Loss of appetite and significant weight loss	(Such as gastrointestinal feeding, parenteral nutrition)		
Vomiting	1 ~ 2 times/24 hours without affecting activities	3 ~ 5 times/24 hours or limited activity	> 6 times within 24 hours or intravenous fluid therapy needed	Due to hypotensive shock, hospitalization or other means of nutrition are required		
Transient (<24 hours)  or intermittent with basically normal food intake		Persistent nausea leading to reduced food intake (24 to 48 hours)	Persistent nausea leading to almost no food intake (> 48 hours) or the need for intravenous fluid therapy	Life threatening (Such as hypotension shock)		
Musculoskeletal ar	nd connective tis	sue				

Organ system symptoms/signs	Grade 1	Grade 2	Grade 3	Grade 4
Myalgia (Non-vaccination site)	Do not affect daily activities	Slightly affect daily activities	Severe muscle pain, severely affecting daily activities	Emergency treatment or hospitalization
Arthritis	Mild pain, accompanied by inflammation, erythema, or joint swelling; but not hindering function	Moderate pain, accompanied by inflammation, erythema, or joint swelling; hindering function, but not affecting daily activities	Severe pain, accompanied by inflammation, erythema, or joint swelling; affecting daily activities	Permanent and/or disabling joint damage
Arthralgia	Mild pain, not hindering function	Moderate pain; needing analgesics and/or pain hindering function, but not affecting daily activities	Severe pain; needing analgesics and/ or pain affecting daily activities	Disabling pain
Nervous System	 			
Headache	Not affecting daily activities, no treatment required	Transient, slightly affecting daily activities, possibly requiring treatment or intervention	Seriously affecting daily activities and requiring treatment or intervention	Intractable, requiring emergency treatment or hospitalization
Syncope	Close to syncope, without losing consciousness (e.g., pre- syncope)	Loss of consciousness, but no treatment is needed	Loss of consciousness, requiring treatment or hospitalization	NA
New-onset convulsions	NA	NA	1 ~ 3 occurrences of convulsion	Prolonged and multiple occurrences of convulsion (e.g., convulsion status) or difficult to control (e.g., intractable epilepsy)
Respiratory system	n			
Cough	Transient, no treatment needed	Continuous cough, effective treatment	Paroxysmal cough, cannot be controlled by treatment	Emergency treatment or hospitalization

Organ system symptoms/signs	Grade 1	Grade 2	Grade 3	Grade 4
Acute bronchospasm	Transient; no treatment required; FEV 1 % is 70% to 80%	Treatment required; return to normal after bronchodilator treatment; FEV 1 % is 50% to 70%	Cannot return to normal after bronchodilator treatment; FEV 1 % is 25% to 50% or continuous intercostal depression	Cyanosis; FEV 1 % <25%; or intubation required
Dyspnea	Dyspnea during exercise	Dyspnea in normal activities	Dyspnea at rest	Dyspnea, requiring oxygen therapy, hospitalization or assisted breathing
Organ system symptoms/signs	Grade 1	Grade 2	Grade 3	Grade 4
Skin and subcutan	eous tissue			
Pruritus at the non-vaccination site (No skin damage)	Slight itching, does not affect or slightly affects daily life	Pruritus affecting daily life	Pruritus making daily life impossible	NA
Abnormal skin and mucosa	Erythema/pru ritus/color change	Diffuse rash/maculopapular rash/xerosis/desqua mation	Blistering/exudation/desqua mation/ulceration	Exfoliative dermatitis involving mucosa, or erythema multiforme, or suspected Stevens- Johnsons syndrome
Mental system	I			
Insomnia*	Mild difficulty falling asleep, not affecting or slightly affecting daily life	Moderate difficulty falling asleep, affecting daily life	Severe difficulty falling asleep, seriously affecting daily life, requiring treatment or hospitalization	NA
Irritation or suppression	Mild irritation or mild suppression	Irritability or drowsiness	Unable to soothe or respond poorly	NA
Mental disorders (Including anxiety, depression, mania, and insanity)	Mild symptoms, no need to see a doctor, or behavior does not affect or slightly	Have clinical symptoms and need medical treatment or behaviors affect daily life	Need to be hospitalized or unable to support daily life	Have a tendency to hurt him/herself or others or acute mental confusion or loss of basic selfcare ability

Organ system symptoms/signs	Grade 1	Grade 2	Grade 3	Grade 4
Detailed symptoms should be reported	affects daily life			
Immune system	I			
Acute allergic reactions**	Local urticaria (blisters), requiring no treatment	Local urticaria requiring treatment or mild angioedema requiring no treatment	Extensive urticaria or angioedema requiring treatment or mild bronchospasm	Allergic shock or life-threatening bronchospasm or laryngeal edema
Others				
Fatigue, asthenia	Do not affect daily activities	Affect normal daily activities	Seriously affect daily activities and cannot work	Emergency treatment or hospitalization
Pain at non-vaccination site (Specify the location when reporting)	Mild pain, not affecting or slightly affecting daily life	Pain affecting daily life	Pain making daily life impossible	Disabling pain, loss of basic self-care ability

Note: FEV1% refers to forced expiratory volume in one second (FEV1) / forced vital capacity (FVC)

Appendix B. Table 4 Grading scale for blood biochemistry

Testing parameter	Grade 1	Grade 2	Grade 3	Grade 4
Liver function (Elevated ALT, AST)	1.25~<2.5 ×ULN	2.5~<5.0×ULN	5.0~<10×ULN	≥10×ULN
Elevated total bilirubin (mg/dL; µmol/L)	1.1~<1.6×ULN	1.6~<2.6×ULN	2.6~5.0×ULN	≥5.0×ULN
Pancreatin (amylase, lipase)	1.1~<1.5×ULN	1.5~<3.0×ULN	3.0~<5.0×ULN	≥5.0×ULN
Creatine phosphokinase (CPK)	1.25~<1.5×ULN	1.5~<3.0×ULN	3.0~<10×ULN	≥10×ULN
Hypernatremia (Na, mmol/L)	146~<150	150~<154	154~<160	≥160
Hyponatremia (Na, mmol/L)	130~<135	125~<130	121~<125	≤120
Hyperkalemia (K, mmol/L)	5.6~<6.0	6.0~<6.5	6.5~<7.0	≥7.0

\* For constipation and insomnia, attention should be paid to the changes before and after vaccination.

\*\* Refers to type I hypersensitivity.

# Refers to other non-vaccination site pains except muscle pain, arthralgia and headache.

Testing parameter	Grade 1	Grade 2	Grade 3	Grade 4
Hypokalemia (K, mmol/L)	3.0~<3.4	2.5~<3.0	2.0~<2.5	<2.0
Hypercalcemia (Ca, mmol/L)	2.65~<2.88	2.88~<3.13	3.13~<3.38	≥3.38
Hypocalcemia (Ca, mmol/L)	1.95~<2.10	1.75~<1.95	1.53~<1.75	<1.53
Hyperglycemia (Glu, mm	nol/L)			
Fasting	6.11~<6.95	6.95~<13.89	13.89~<27.75	≥27.75
Non-fasting	6.44~<8.89	8.89~<13.89	13.89~<27.75	≥27.75
Hypoglycemia (Glu, mmol/L)	3.05~<3.55	2.22~<3.05	1.67~<2.22	<1.67

Note: ULN refers to the upper limit of the normal range.

# Appendix B. Table 5 Grading scale for blood routine tests

Testing parameter/Grading	Grade 1	Grade 2	Grade 3	Grade 4
Increased white blood cells (WBC, 10  /L)	11~<13	13~<15	15~<30	≥30
Decreased white blood cells (WBC, 10  /L)	2.000~2.499	1.500~1.999	1.000~1.499	<1.000
Decreased lymphocytes (LY, 10  /L)	0.75~1.00	0.5~0.749	0.25~0.49	<0.25
Decreased neutrophils (ANC, 10  /L)	0.800~1.000	0.600~0.799	0.400~0.599	<0.400
Eosinophils (Eos, 10  /L)	0.65~1.5	1.51~5.0	>5.0	Hypereosinophilic syndrome
Thrombocytopenia (PLT, 10  /L)	125~140	100~124	25~99	<25
Low hemoglobin (g/dL)				
Male	10.0~10.9	9.0~<10.0	7.0~<9.0	<7.0
Female	9.5~10.4	8.5~<9.5	6.5~<8.5	<6.5

# Appendix B. Table 6 Grading scale for urine routine tests

Testing parameter	Grade 1	Grade 2	Grade 3	Grade 4
Urine protein (PRO) (Urine test strip testing)	1+	2+	3+ or higher	NA
Urine glucose (Urine test strip testing)	Trace ~ 1+ or ≤250mg	2+ or >250~≤500mg	>2+ or >500mg	NA
Red blood cells (microscopic examination)  [The number of red blood cells (rbc/hpf) per high-power field of view (excluding female menstrual periods)]	6~<10	≥10	Gross hematuria with or without blood clots; or barrel-type urinary erythrocyte; or in need of treatment	Emergency treatment or hospitalization

# Appendix B. Table 7 General principles for grading of other adverse events

Grade 1	Grade 2	Grade 3	Grade 4	Grade 5
Mild: Short-term (<48h) or slight discomfort, which does not affect activity, and no treatment is needed	Moderate: Mild or moderate limitation of activity, which may require medical attention, does not require or only requires mild treatment	Severe: Obviously restricted activity, requiring medical attention and treatment, possibly requiring hospitalization	Critical: Possibly life-threatening; serious limitation of activity, requiring intensive care	Death

Note: refer to Common Terminology Criteria for Adverse Events (CTCAE) Version 5.0 for grading of advrse events thyroid function (T3, T4, thyrotropin) and coagulation function (PT, APTT, TT, FIB).

# Appendix C FDA Toxicity Grading Scale in Preventive Vaccine Clinical Trials

These guidelines for toxicity grading scales are primarily intended for healthy adult and adolescent volunteers.

#### **Assessment of intensity**

The intensity of AEs or SAEs will be graded by the investigator. For further guidance please refer to guideline "US FDA Guidance for Industry. Toxicity Grading Scale for Healthy Adult and Adolescent Volunteers Enrolled in Preventive Vaccine Clinical Trials". Where specific guidance for an adverse event term is not provided, the following general approach should be followed:

- Grade 1 Mild; does not interfere with the subject's usual function.
- Grade 2 Moderate; interferes to some extend with the subject's usual function.
- Grade 3 Severe; interferes significantly with the subject's usual function.
- Grade 4 Potentially Life threatening; life-threatening consequences, urgent intervention required.

Please also refer to the intensity tables given in the guideline for intensity of clinical and laboratory abnormalities to be reported as AEs:

• Guideline Section III. A for assessment of clinical abnormalities (local and systemic)

#### **Local Reactions**

Redness and swelling will be measured and recorded in centimeters and then categorized during analysis as absent, mild, moderate, or severe based on the grading scale in Table 1.

Pain at the injection site will be assessed by the trial subject as absent, mild, moderate, or severe according the grading scale in Table 1.

Appendix C. Table 1 Local reaction grading scale

	Mild (Grade 1)	Moderate (Grade 2)	Severe (Grade 3)	Potentially Life Threatening (Grade 4)
Pain at the injection site	Does not interfere with activity	Interferes with activity	Prevents daily activity	Emergency room visit or hospitalization for severe pain
Redness	2.5 cm to 5.0 cm	>5.0 cm to 10.0 cm	>10 cm	Necrosis or exfoliative dermatitis
Swelling	2.5 cm to 5.0 cm	>5.0 cm to 10.0 cm	>10 cm	Necrosis

# **Systemic events**

Symptoms of vomiting, diarrhea, headache, fatigue, chills, new or worsened muscle pain, and new or worsened joint pain will be assessed by the participant as absent, mild, moderate, or severe according to the grading scale in Table 2.

# Appendix C. Table 2 Systemic event grading scale

Mild	Moderate	Severe	Potentially Life Threatening
(Grade 1)	(Grade 2)	(Grade 3)	(Grade 4)

Vomiting	1-2 times in 24 h	>2 times in 24 h	Requires IV hydration	Emergency room visit or hospitalization for hypotensive shock
Diarrhea	2 to 3 loose stools in 24 h	4 to 5 loose stools in 24 h	6 or more loose stools in 24 h	Emergency room visit or hospitalization for severe diarrhea
Headache	Does not interfere with activity	Some interference with activity	Prevents daily routine activity	Emergency room visit or hospitalization for severe headache
Fatigue/ tiredness	Does not interfere with activity	Some interference with activity	Prevents daily routine activity	Emergency room visit or hospitalization for severe fatigue
Chills	Does not interfere with activity	Some interference with activity	Prevents daily routine activity	Emergency room visit or hospitalization for severe chills
New or worsened muscle pain	Does not interfere with activity	Some interference with activity	Prevents daily routine activity	Emergency room visit or hospitalization for severe new or worsened muscle pain
New or worsened joint pain	Does not interfere with activity	Some interference with activity	Prevents daily routine activity	Emergency room visit or hospitalization for severe new or worsened joint pain

#### **Fever**

Fever is defined as an oral temperature of  $\ge 38.0$  °C. Temperature will be measured and recorded to 1 decimal place and then categorized during analysis according to the scale shown in Table 3.

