# Please note:

Diary cards will be the only source document allowed for remote collection of solicited local and systemic reactions (including body temperature measurements). The following additional rules apply to the documentation of safety information collected by diary card:

- o Diary cards should be reviewed with the subject.
- No corrections or additions to the diary card will be allowed after it is reviewed with the investigator/designee.
- O Any data that are identified as implausible or incorrect, and confirmed by the subject to be a recording error should be corrected by the subject on the diary card (the correction should include a single strikethrough line and should be primeed and dated by the subject).
- Any blank or illegible fields on the diary card not otherwise corrected as above will be missing in the eCRF.
- The study site should enter all readable entries on the diary card into the eCRF.
- O Any newly described solicited safety information should be added to the diary card by the subject and primeed and dated. Any new unsolicited safety information would be recorded in the subject source document as a verbally reported event and therefore captured as an AE and recorded in the AE eCRF.
- Starting on the day of vaccine/placebo administration, the subject will check for specific types of events at the vaccination site (solicited local reactions), any specific generalized symptoms (solicited systemic reactions), body temperature (axillary), any other symptoms or change in the subject's health status, and any medications taken. These solicited reactions and body temperature will be recorded in the diary. Assessments should preferably take place in the evening at day's end using the same method of measurement every day.
- Temperature measurement is to be performed using the thermometer provided by the study site. If the subject feels unusually hot or cold during the day, the subject should

- check his/her temperature. The highest body temperature measured that day should be recorded on the diary card.
- The measurement of solicited local reactions (pain/tenderness, erythema/redness, and induration/swelling) is to be performed using the ruler provided by the study site. If multiple measurements are taken during the day, the highest measured value should be recorded on the diary card.

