# 13.1.4 Primary endpoints

All AEs will be coded using the most recent version of Medical Dictionary for Regulatory Activities (MedDRA version 23.0) coding system to get a system organ class (SOC) and preferred term (PT) for each AE.

AEs and solicited reactions will be summarized using the Safety Set. In general, safety parameters will be analyzed by grouping and for each immunization, i.e., for:

- Day 1-21 (pre-boost)
- Day 21(post-boost) 28

Additionally, AEs and reactions will be summarized for all dose levels combined for each type.

For each analysis, the number and percentage of subjects reporting at least one AE will be summarized by PT nested within SOC for each of the following AE types using the Safety Set:

- Any AE
- Related AE
- >Grade 3 AE
- Related AE >Grade 3
- AE leading to withdrawal
- Any SAE
- Related SAE

Moreover, the number and percentage of subjects with any AE will be summarized by worst grade by PT nested within SOC.

During 14 days post vaccination (including the day of BNT162b1/placebo vaccination), evaluate reactogenicity by daily solicited reactions, including local reactions (vaccination site: pain/tenderness, erythema/redness, induration/swelling) and systemic reactions (nausea, vomiting, diarrhea, headache, fatigue, myalgia, arthralgia, chills, loss of appetite, malaise, and fever), as well as non solicited AE. In addition, body temperature (axillary) was collected as the indicator of reactogenicity (fever was defined as axillary temperature ≥37.3 °C or oral temperature ≥38 °C).

For each solicited reaction (including fever), the percentage of subjects will be aggregated according to the severity of the events and the total number of subjects within 14 days of each vaccination/placebo.

Local and systemic responses were recruited within 14 days after each vaccination, non-solicited TEAE within 21 days after the prime vaccination and 28 days after boost vaccination, and IMP-

related AE were studied after 28 days. Adverse reaction classification criteria given in appendix B and appendix C were used for classification. During the study period, AEs uninvolved in the appendix grading scales will be graded clinically by the investigator according to the criteria in Section 10.3.1.

For each immunization, the number and percentage of subjects reporting at least one local reaction or systemic reaction will be summarized for each of the following types using the Safety Set:

- Any local reactions or systemic reactions

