7.5 Exploratory analyses

7.6 Safety Analyses

7.6.1 Adverse Events

All AEs will be coded using the recent version of MedDRA Version 23.0, and be summarized by SOC and PT. Additionally, solicited AEs, including systematic AEs and local AEs predefined in the protocol, will be summarized. The severity of AEs will be analyzed under China NMPA Guidance (Refer to Appendix B in the protocol: *NMPA Guidance for Adverse Events Grading Scale for Preventive Vaccine Clinical Trials in China*), and that of adverse reactions will also be analyzed under US Food and Drug Administration (FDA) Guidance (Refer to Appedix C in the protocol: *FDA Toxicity Grading Scale in Preventive Vaccine Clinical Trials*) in addition to China NMPA guidance.

This study is mainly to analyze Treatment Emergent Adverse Events (TEAEs), which are defined as any AEs with an onset on or after the first immunization (if the AE was absent before the first immunization) or worsened after the first immunization (if the AE was present before the first immunization). The Non-TEAEs occur before the first immunization will not be included in the analysis, but will be listed. Unless particularly stated, AEs mentioned in below text are TEAEs.

All solicited AEs, including systematic and local AEs, will be graded based on the criteria given in "NMPA Guidance for Adverse Events Grading Scale for Preventive Vaccine Clinical Trials in China". And all related systematic and local reactions will be graded at the same time according to "US FDA Guidance for Industry. Toxicity Grading Scale for Healthy Adult and Adolescent Volunteers Enrolled in Preventive Vaccine Clinical Trials". The solicited systematic and local reactions will be analyzed based on both NMPA and US FDA guidance.

The episodes of AEs, number and percentages of subjects who experience at least one TEAE as follows will be presented by group:

- Overall Summary of Adverse Events
- > Any TEAEs by SOC and PT
- Related TEAEs by SOC and PT
- Unrelated TEAEs by SOC and PT
- > Any TEAEs by Solicited and Unsolicited AEs
- Related TEAEs by Solicited and Unsolicited AEs
- Unrelated TEAEs by Solicited and Unsolicited AEs
- ➢ Grade≥3 TEAEs by SOC and PT, according to China NMPA guidance

- ➢ Grade≥3 related TEAEs by SOC and PT, according to China NMPA guidance
- ➢ Grade≥3 Solicited Systematic and Local Reactions, according to China NMPA guidance
- ➢ Grade≥3 Solicited Systematic and Local Reactions, according to US FDA guidance

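### Diary temperatures are axillary, but the FDA fever scale is oral and no conversion is specified; applied literally, readings within 0.2 °C below each cut-off are graded one FDA level too low

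*Protocol*

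**What the plan says.** **Route of measurement.** The diary-card instructions in Protocol 9.3.4 ask the subject to record "body temperature (axillary), any other symptoms or change" in health status. Protocol 13.1.4 repeats that "body temperature (axillary) was collected as the indicator of reactogenicity". Diary cards are the only source allowed for remote collection of solicited reactions.

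**FDA scale.** Protocol Appendix C states: "Fever is defined as an oral temperature of" 38.0 °C or above. The next sentence is the grading instruction: "Temperature will be measured and recorded to 1 decimal place and then categorized during analysis according to the scale shown in Table 3". Table 3 there gives Grade 1 as 38.0–38.4, Grade 2 as 38.5–38.9, Grade 3 as 39.0–40.0 and Grade 4 as above 40.0 °C. It has no axillary column.

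**NMPA scale.** Protocol Appendix B Table 2 is written for axillary temperature, with Grade 1 starting at 37.3 °C. Its footnote allows conversion where needed and gives the relation: "Generally, oral temperature = axillary temperature + 0.2 °C".

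**Use of both scales.** SAP 7.6.1 says: "The solicited systematic and local reactions will be analyzed based on both NMPA and US FDA guidance". It plans a separate Grade 3 or higher table of solicited reactions under each guidance. Under SAP 7.1.2, a related event that reaches NMPA Grade 1 but not FDA Grade 1 does not count as an adverse event under FDA guidance.

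**Fever definition.** Protocol 10.1.2 uses axillary 37.3 °C or more alone. Protocol 13.1.4 and the synopsis pair axillary 37.3 °C with oral 38.0 °C.

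**The concern.** A reading taken by one route is to be placed on a scale defined for another, and the only available relation between the routes is never applied to that step. Axillary values sit below oral values on the protocol's own relation, so any error runs one way: FDA-graded fever can be too low, never too high.

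Two planned outputs are exposed. First, a related axillary reading just under 38.0 °C would be NMPA Grade 1 yet have no FDA grade, and SAP 7.1.2 would remove it from the FDA analysis. Second, a reading just under 39.0 °C would be missing from the FDA table of Grade 3 or higher reactions. With about 24 subjects per dose group, one reclassified subject moves a rate by 1/24 = 4.2 percentage points.

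The plan also allows two programmers to produce different FDA fever tables, one converting and one not, with both complying with the text.

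**Working it through.** **Inputs.** Route: axillary (Protocol 9.3.4, 13.1.4). FDA bands: Appendix C Table 3. Relation: oral = axillary + 0.2 °C (Appendix B Table 2 footnote). Recording precision: 0.1 °C (Appendix C). The plan states no figure of its own on this point, so there is none to reproduce.

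**Method.** Each axillary reading *t* from 37.0 to 41.0 °C, in steps of 0.1, was graded twice on Table 3: as measured, *G(t)*, which is the literal instruction, and as oral-equivalent, *G(t + 0.2)*. The readings where the two grades differ are:

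| Axillary reading (°C) | Oral-equivalent (°C) | FDA grade, unconverted | FDA grade, converted | NMPA temperature band |
|---|---|---|---|---|
| 37.8, 37.9 | 38.0, 38.1 | none | 1 | 1 |
| 38.3, 38.4 | 38.5, 38.6 | 1 | 2 | 2 |
| 38.8, 38.9 | 39.0, 39.1 | 2 | 3 | 3 |
| 39.9, 40.0 | 40.1, 40.2 | 3 | 4 | 3 (4 only if 39.5 or above for more than 3 days) |

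**Result.** Eight readings change, each by exactly one grade upward on conversion. No reading falls. From 37.8 to 40.0 °C there are (40.0 − 37.8)/0.1 + 1 = 23 readings, so 8 of 23 are affected. All eight lie in the 0.2 °C just below a cut-off. Readings at or just above a cut-off (38.0, 38.1, 38.5, 38.6, 39.0, 39.1, 40.1, 40.2) keep their grade.

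**Paired definition.** On the same relation, axillary 37.3 °C is oral 37.3 + 0.2 = 37.5 °C. That is 38.0 − 37.5 = 0.5 °C below the oral cut-off it is joined to in Protocol 13.1.4, so the two halves do not describe the same event.

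**Sensitivity to the relation.** If the paired cut-offs were instead read as equivalents, the implied difference would be 38.0 − 37.3 = 0.7 °C. Repeating the enumeration with 0.7 changes 24 readings: 20 by one grade and 4 (37.8, 37.9, 38.3, 38.4) by two. The protocol does not state 0.7 °C as a conversion. The run shows only that the answer depends on which relation is used, so the plan has to name one.

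**The case against.** **A conversion may exist out of sight.** Silence is not proof that raw values are used. The Appendix B footnote permits conversion, and grading axillary data on an oral scale is arguably the case it was written for. Protocol 10.3.1 has the investigator grade on both scales, and SAP 7.1.2 speaks of a null FDA grade in the EDC, which suggests grades are stored there. The eCRF and Data Management Plan listed in SAP 2.1 are not available here. This stands as a limit: the documents show that conversion is not prespecified, not that it will be omitted. It does not remove the point, because Appendix C places the categorisation at analysis and gives no conversion step.

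**Not every temperature is shown to be axillary.** Only the diary route is stated. On-site vital signs (Protocol 9.1.5) name no route. This stands.

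**The primary safety result is not compromised.** A reader might infer that the primary fever endpoint is wrong. The documents do not support that. Solicited fever is defined as axillary 37.3 °C or more in Protocol 10.1.2, all solicited events are graded on the NMPA scale, and neither changes with conversion. FDA grading is an additional presentation of related reactions.

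**Bridging.** A reader might also infer that the comparison with the US data is biased. The US summary in Protocol 4.2.4.1 reports fever at 38.0 °C or more without a route, no passage names the FDA table as the comparator, and the SAP describes no analysis against foreign data. That inference goes beyond the text.

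**Two scales already imply two fever definitions.** This is partly right, since SAP 7.1.2 anticipates events that count under one guidance only. The single definition joined by an or in Protocol 13.1.4 still needs separating.

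**Conclusion.** The point holds as a gap in specification with a calculable consequence. Followed literally, the plan under-grades eight axillary readings by one FDA level, and related 37.8–37.9 °C events leave the FDA-guidance analysis. This rests on three assumptions: the values entering FDA grading are the axillary diary readings, no conversion is made elsewhere, and the protocol's general +0.2 °C relation is adequate.

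It would be too strong to say that FDA-graded fever will be wrong, or to treat 8 of 23 as an error rate. That figure counts thermometer steps in one window. The documents give no temperature distribution, so the number of subjects affected cannot be computed. NMPA grading and axillary 37.3 °C fever stand as they are. The matter deserves correction because the error has one direction, the affected tables are planned outputs and the remedy is small.

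**What to change.** **SAP 7.6.1, before unblinding.** State the route of every temperature used. State that, for the FDA-graded fever tables, axillary readings are converted to oral-equivalent by the protocol's +0.2 °C relation, and that NMPA grading uses the raw axillary value. Show the unconverted FDA grading as a sensitivity table. State also whether FDA grades are derived at analysis or taken from the EDC.

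**Protocol 13.1.4 and the matching synopsis text.** Replace the joined definition with two labelled outcomes: NMPA fever (axillary 37.3 °C or more) and FDA fever (oral-equivalent 38.0 °C or more).

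**Scope.** Confine the conversion to the analysis tables. The dose-limiting-toxicity criteria in Protocol 6.6 and SAP 4.1.3 include fever above 40.0 °C without a route and Grade 4 events without a scale, and conversion moves 39.9–40.0 °C to FDA Grade 4. The sponsor must reconcile those passages; no threshold is proposed here.

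**Cost.** One derived variable, one extra table and a few sentences, with no new data collection. FDA fever rates and grades may rise slightly.
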